14.6 Audits and inspections

Authorized representatives of Sponsor may perform audits at the research clinic, including source data verification (SDV). The purpose of an audit is to systematically and independently examine all study-related activities and documents, to determine whether these activities were conducted, and data were recorded, analyzed, and accurately reported according to the protocol, ICH-GCP guidelines and any applicable regulatory requirements.

14.7 Insurance

Subjects will be covered under Swedish Match AB's liability insurance policy through IF insurances. The certificate of insurance and an information leaflet containing essential information about the insurance coverage can be provided upon request. The participating subjects are also protected in accordance with national regulations, as applicable. CTC has a company insurance covering services performed by CTC.

15 STUDY MANAGEMENT

15.1 Training of study site personnel

Before enrolment of the first study subject a Sponsor representative or delegate will perform a study initiation visit at the research clinic. The requirements of the CSP and related documents will be reviewed and discussed, and the investigational staff will be trained in any study specific procedures and system(s) utilized.

It is the responsibility of the Investigator to ensure that all personnel involved in the study are fully informed of all relevant aspects of the study and have a detailed knowledge of and training in the procedures that are to be executed by them. Any new information of relevance to the performance of this study must be forwarded to the staff involved in a timely manner.

The Investigator will keep a list of all personnel involved in the study together with their function and study related duties delegated. A Curriculum Vitae will be available for key staff to whom study-specific duties are delegated.

15.2 Clinical monitoring

The Sponsor is responsible for securing agreement from all involved parties to ensure direct access to all study related sites, source data/documents, and reports for the purpose of monitoring and auditing by the Sponsor, and inspection by domestic and foreign regulatory authorities.

As defined in the risk-based monitoring (RBM) plan, approved by the Sponsor and provided separately, the responsible Monitor will periodically visit the study site at times agreed upon by the Investigator and the Monitor. Adaptations related to the on-site monitoring plan, when it is impossible or inappropriate to follow due to the COVID-19 pandemic, may be required such as supplementation with (additional/increased) centralised monitoring and central review of data if considered possible and meaningful. Results of adjusted monitoring/review measures should be reported to the Sponsor in monitoring reports and in the CSR. At the time of each monitoring visit, the role of the Monitor is (but not limited to) to:

- provide information and support to the investigational team.
- confirm that facilities and resources remain acceptable.
- confirm that the investigational team is adhering to the CSP, applicable SOPs, guidelines, manuals and regulatory requirements.
- verify that data are being accurately and timely recorded in the eCRFs and that IP accountability checks are being performed.
- verify that data in the eCRF are consistent with the clinical records (SDV) in accordance with the RBM plan.
- verify that the correct informed consent procedure has been adhered to for participating subjects.
- ensure that withdrawal of informed consent to the use of the subject's biological samples will be reported and biological samples are identified and disposed of/destructed accordingly, and that this action is documented and reported to the subject.
- verify that AEs are recorded and reported in a timely manner and according to the CSP.
- Raise and escalate any serious quality issues, serious GCP breach and any data privacy breach to the Sponsor.

Centralized monitoring will also be performed continuously by study team members at CTC in accordance with the RBM plan.

When the study has been completed and all queries have been resolved and the database has been locked, the Monitor will perform a close-out visit.

15.3 Source data documents

A separate Origin of Source Data List will be generated for each site before start of enrolment, specifying the location of the source of derived information appearing in the CRF. This document must be signed by the Principal Investigator and the Monitor to confirm agreement before start of recruitment.

Source documents are all documents used by the Investigator or hospital that relate to the subject's medical history, that verifies the existence of the subject, the inclusion and exclusion criteria, and all records covering the subject's participation in the trial. They include laboratory notes, memoranda, material dispensing records, subject files, etc. The eCRF may constitute source data if clearly defined in the Origin of Source Data List.

The Investigator should guarantee access to source documents to the Monitor and the IECs, if required.

15.4 Study agreements

The Principal Investigator must comply with all the terms, conditions, and obligations of the Clinical Study Agreement for this study.

Agreements between Sponsor and CTC must be in place before any study-related procedures can take place, or subjects be enrolled.

15.5 Study timetable and end of study

The study is expected to start in Q3 2020 and to be completed by Q4 2020.

A subject is considered to have completed the study if he/she has completed all visits in the study including visit 8, telephone follow-up.

The end of the study is defined as the last visit of the last subject participating in the study.

15.6 Termination of the study

The Sponsor reserves the right to terminate this study prematurely for any reasonable cause. Conditions that may warrant study termination include, but are not limited to:

• A decision by the Sponsor to suspend or discontinue development of the IP.

If the study is prematurely terminated or suspended for any reason, the Investigator should promptly inform the study subjects and should assure appropriate follow-up for the subjects.

15.7 Reporting and publication

15.7.1 Clinical study report

A clinical study report (CSR), in compliance with ICH-E3, describing the conduct of the study, any statistical analyses performed, and the results obtained, will be prepared by CTC. The report will be reviewed and approved by, as a minimum, the Principal Investigator, the Statistician and the Sponsor.

Results for the exploratory comparison of sampling technique between plasma sampling and DBS for nicotine concentrations will be reported separately.

15.7.2 Confidentiality and ownership of study data

Any confidential information relating to the IP or the study, including any data and results from the study, will be the exclusive property of the Sponsor. The Investigator and any other persons involved in the study are responsible for protecting the confidentiality of this proprietary information belonging to the Sponsor.

15.7.3 Publication

The results from this study may be submitted for publication at the discretion of the Sponsor.

15.8 Archiving

The Principal Investigator is responsible for maintaining essential documents, (as defined in ICH E6 GCP, Section 8) for 10 years after finalisation of the CSR. This includes any original source documents related to the study, the Subject Identification List (providing the sole link between named subject source records and anonymous eCRF data), the original signed ICFs and detailed records of disposition of IP.

It is the responsibility of the Sponsor to inform the Investigator/institution as to when these documents no longer need to be retained.

The Sponsor will archive the TMF in accordance with ICH E6 GCP, Section 8 and applicable regulatory requirements.

The data from the eCRFs will be sent to the Sponsor and a copy will be sent to the clinic and filed in the Investigator Study File for archiving for 10 years after finalisation of the CSR.

The completed eCRF are the sole property of the Sponsor and should not be made available in any form to third parties, except for authorized representatives of appropriate Health/Regulatory Authorities, without written permission from the Sponsor.

16 DATA MANAGEMENT

The data management routines include procedures for handling of the eCRF, database set-up and management, data entry and verification, data validation, QC of the database, and documentation of the performed activities including information of discrepancies in the process. The database, data entry screens, and program will be designed in accordance with the CSP.

Data validation/data cleaning procedures are designed to assure validity and accuracy of clinical data. These procedures consist of computerized online edit checks identifying e.g. data values that are outside the allowed range and SAS-programmed offline checks on data exports. All study-specific and standard data validation programming will be tested in a separate testing environment prior to use on production data.

Detailed information on data management will be described in a study-specific Data Management Plan (DMP).

16.1 The web-based eCRF

Clinical data will be entered into a 21 CFR Part 11-compliant eCRF (ViedocTM) provided by PCG Solutions AB. The eCRF includes password protection, and internal quality checks such as automatic range checks, to identify data that appear inconsistent, incomplete, or inaccurate. Clinical data will be entered directly from the source documents or at bedside (if the eCRF data constitutes source data). Source data are to be defined at the site before inclusion of the first subject (Section 15.3).

Authorized site personnel designated by the Investigator will complete data collection. Appropriate training and security measures will be completed with the Investigator and all

authorized trial site personnel prior to the trial being initiated and any data being entered into the system for any study subject.

16.2 The entering of data into the eCRF

All entries, corrections, and alterations in the eCRF are to be made by the Investigator or designated site personnel. Neither the Monitor nor any other study team member besides site personnel may enter data in the eCRF. All data should be entered in English. The eCRFs should be completed as soon as possible during or after the subject's visit. If some assessments are not done, or if certain information is not available, not applicable or unknown, the Investigator or assigned clinical staff should record such information in the eCRF.

The Investigator must verify that all data entries in the eCRFs are accurate and correct and will be required to electronically sign off the clinical data. This will be performed by means of the Investigator's unique UserID and password; date and time stamps will be added automatically at the time of electronic signature.

16.3 The query process

The monitor will review the eCRFs and evaluate them for completeness and consistency. Data in the eCRF will be compared with the respective source documents to ensure that there are no discrepancies for critical data as described in the RBM plan.

If corrections are needed, queries will be raised within the eCRF, either as a result of built-in edit checks or manually raised by the monitor. An appropriate member of the site staff will answer the queries in the eCRF either by correcting the data or by entering a response to the query. The monitor will either approve the answer/correction or re-issue the query.

16.4 Audit trail

All entries in the eCRF will be fully recorded in a protected audit trail. Once clinical data have been saved, corrections to the data fields will be audit trailed, meaning that the reason for change, the name of the person who made the change, together with time and date will be logged.

16.5 External data

External data consists of data that are not recorded in the eCRF. Data may be received in electronic format. Key variables are defined in order to uniquely identify each sample record. File and data formats are agreed with the external data provider.

16.6 Medical coding

Medical coding will be performed by trained personnel at CTC. AEs and medical/surgical history verbatim terms will be coded using the Medical Dictionary of Regulatory Activities (MedDRA; latest version available at start of coding). Prior and concomitant medications will be coded according to the World Health Organisation (WHO) Anatomic Therapeutic Chemical (ATC) classification system. All coding will be approved by Sponsor prior to database lock.

16.7 Database lock

When all data have been entered and discrepancies solved, clean file will be declared, the database will be locked, and the data will be analyzed.

17 STATISTICAL METHODS AND DETERMINATION OF SAMPLE SIZE

The principal features of the statistical analysis to be performed are described in this section. A more technical and detailed elaboration of the principal features will be presented in a separate Statistical Analysis Plan (SAP), which will be signed and approved prior to database lock.

17.1 General

Continuous data will be presented with descriptive statistics in terms of evaluable and missing observations, arithmetic mean, standard deviation (SD), median, minimum and maximum value, Q1-Q3 (interquartile range [IQR]). In addition, for the parameters AUC and C_{max} the geometric mean and coefficient of variation (CV) will be presented.

Categorical data will be presented as counts and percentages. When applicable, summary data will be presented by treatment, and by assessment time. Individual subject data will be listed by subject number, treatment, and, where applicable, by assessment time.

All descriptive summaries and statistical analyses will be performed using SAS Version 9.4 or later (SAS Institute, Inc., Cary, NC).

Baseline will be defined as the visit with last data collection point prior to the first administration of IP.

All hypothesis testing will use a significance level of 5%.

No imputation of missing data will be performed.

17.2 Determination of sample size

No formal sample size calculation has been performed for this study. However, the proposed sample size is considered sufficient to provide adequate information for the study objectives.

The sample size of 32 evaluable subjects is assumed to be enough to address the hypothesis.

Approximately 42 subjects will be screened to achieve 36 randomized subjects and 32 fully evaluable subjects (assuming a drop-out rate of 10%).

17.3 Analysis data sets

17.3.1 Full analysis set

The Full Analysis Set (FAS) will consist of all subjects who have been randomized and received at least one dose of IP and who has at least one post-baseline assessment of efficacy data. This population will be used as the Safety analysis set.

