11.6.3 Time period and frequency for collecting adverse events

All AEs (including SAEs) will be collected from the start of IP administration until the endof-study visit.

Any AE with start date on the day of IP administration must be recorded with start time.

At the end-of-study visit, information on new AEs or SAEs, if any, and stop dates for ongoing during events must be recorded as applicable.

Investigators are not obligated to actively seek AEs or SAEs after conclusion of the study participation. However, if the Investigator learns of any SAE, including a death, at any time after a participant has been discharged from the study, and he/she considers the event to be reasonably related to the study intervention or study participation, the Investigator must promptly notify the Sponsor.

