17.3.3 Additional analysis datasets

Additional datasets may be created as needed for exploratory analyses.

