17.8 Analysis of Adverse events

An overview of all AEs, including SAEs, intensity, and deaths will be presented by SOC and PT.

Incidence of AEs and SAEs will be summarized by SOC and PT by treatment.

All AE data will be listed subject and treatment include the verbatim term entered by the Investigator.

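### The safety set is the FAS, which requires a post-baseline efficacy assessment, so a dosed subject who stops before any such assessment drops out of the AE incidence tables

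*Protocol*

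**What the plan says.** Section 17.3.1 of the protocol defines the FAS by three joint conditions: the subject was randomized, was dosed at least once, and has "at least one post-baseline assessment of efficacy data. This population will be used as the Safety analysis set". The second sentence of that quote makes the FAS the safety population.

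No other section sets up a population of all dosed subjects. Section 17.3.2 is the PK analysis set. Section 17.3.3 allows further sets, but for a different purpose: "Additional datasets may be created as needed for exploratory analyses".

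On AEs, section 11.6.3 starts the clock at dosing: "All AEs (including SAEs) will be collected from the start of IP administration". Section 17.8 gives the summaries ("Incidence of AEs and SAEs will be summarized by SOC and PT by treatment") and the listing ("All AE data will be listed subject and treatment include the verbatim term entered by the Investigator"). It names no analysis set for either, so the set that 17.3.1 designates for safety is the one a programmer would use for the incidence tables.

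**The concern.** A safety population should be fixed by exposure alone. Here it also depends on a later assessment, and a reaction to the product is one reason why that assessment might be missing. Section 9.8.1 itself lists a significant AE among the reasons for discontinuation. A subject lost in this way takes the event out of the numerator and the exposure out of the denominator.

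The condition is also unclear. The endpoints in section 7 are PK, nicotine extraction, urge to snus on a VAS, pulse rate and the dried-blood-spot comparison. None is called efficacy, so the protocol does not say which assessment admits a subject to the safety set.

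What is at stake is the accuracy of the AE incidence tables. The primary comparison is unaffected, because section 17.5.1 runs it on the PK analysis set.

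**Working it through.** **The plan's own figure.** Section 17.2 gives 32 evaluable subjects, 10% drop-out and 36 randomized. 32 / (1 − 0.10) = 35.6, which rounds up to 36. The figure reproduces, and 36 is used below as the number dosed.

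**Who can be lost.** The set is defined per subject, not per visit. In this six-period crossover, one qualifying assessment at any visit keeps the subject in for all visits. Exclusion therefore requires a permanent stop at the first product, with no qualifying assessment obtained. How early depends on what counts as efficacy data:

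| Reading of efficacy data | First scheduled post-dose time | Protocol section |
|---|---|---|
| Urge-to-snus VAS | 2 min | 11.4.2 |
| Plasma nicotine | 5 min | 11.3.1 |
| Pulse rate | 5 min | 11.5.1 |
| Extraction from the used pouch | 60 min | 11.4.1 |

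If any of these suffices, the window is the first 2 minutes at the first treatment visit. It widens only if the VAS is held not to count.

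**Effect of losing one subject who had the event.** Let m of 36 dosed subjects have a given event.

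- All dosed: m/36.
- After exclusion: (m − 1)/35.
- Drop: m/36 − (m − 1)/35 = (35m − 36m + 36)/1260 = (36 − m)/1260.

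| m | All dosed | After exclusion | Drop (percentage points) |
|---|---|---|---|
| 1 | 1/36 = 2.8% | 0/35 = 0% | 35/1260 = 2.8 |
| 12 | 12/36 = 33.3% | 11/35 = 31.4% | 24/1260 = 1.9 |
| 18 | 18/36 = 50.0% | 17/35 = 48.6% | 18/1260 = 1.4 |

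The 2.8 points is thus the maximum, reached when the excluded subject is the only one with the event.

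**Effect of losing one subject without the event.** Incidence moves from m/36 to m/35, a rise of m/1260. For m = 12 that is 12/1260 = 1.0 point upwards.

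**Several subjects.** The protocol does not give the number k of dosed subjects without a qualifying assessment, so k is an assumption. If all k had the event and nobody else did:

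| k (assumed) | All dosed | Safety set as defined |
|---|---|---|
| 1 | 1/36 = 2.8% | 0/35 |
| 2 | 2/36 = 5.6% | 0/34 |
| 3 | 3/36 = 8.3% | 0/33 |

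**Which column.** Section 17.8 summarizes by treatment, and a subject lost in this way has taken one product only. Each exclusion therefore touches one product's column. The 36 assumes that all subjects received that product. In a column of n subjects the maximum is 1/n, for example 1/32 = 3.1 points with the 32 evaluable subjects.

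**The case against.** The strongest reply is that almost nobody could be lost. Dosing is supervised at the clinic (section 10.7), subjects have used snus for at least a year (section 9.4), the first VAS is due at 2 minutes, and one assessment at any visit is enough. The effects reported for the similar ZYN Dry product are salivation, nausea and dyspepsia (section 6.3), and nothing in the protocol points to permanent stops within 2 minutes. This stands as to size. It does not make the definition sound, since the 2-minute limit holds only if the VAS counts, and the protocol does not say that it does.

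A second reply is that the SAP, which is not among the documents available here, may define the term or the set. It may, but the protocol does not leave the safety population open: it names one.

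Several stronger readings are tempting and are not supported:

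- **The events vanish from the report.** Section 17.8 promises an overview of all AEs and a listing of all AE data, and names no set for either. Section 9.8.2 has discontinuing subjects asked about AEs, and section 11.6.9 requires SAE reporting whatever the analysis set. The loss concerns the incidence tables and their denominators.
- **The bias is always downward.** It is downward only when the excluded subject had the event. Excluding a subject without it raises incidence.
- **The vague condition could be applied selectively.** The study is open, but nothing in the protocol indicates this, and section 17 requires the SAP to be signed before database lock.
- **Everyone who stops at Visit 2 is dropped, because section 17.1 defines baseline as a visit.** The wording is loose, but no section says that post-dose assessments at Visit 2 are not post-baseline.

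**Conclusion.** The point holds as a fault in the set definition, with a small expected effect. As written, the safety set can omit a dosed subject who stops permanently at the first product before any qualifying assessment. Where a reaction caused the stop, incidence for that product is understated by at most about 2.8 percentage points per such subject with 36 dosed, and by less for a common event (1.4 points when 18 of 36 have it). The number of such subjects is unknown. It is probably very small if the 2-minute VAS qualifies, and could be larger if only a later measurement does. Section 7 contains no safety objective and the primary analysis uses another set, so no efficacy or PK conclusion depends on this. It should still be corrected, because the correction is trivial and the present rule ties the safety denominator to what happens after dosing.

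**What to change.** In section 17.3.1, delete the sentence that makes the FAS the safety set. Add a separate Safety analysis set: all subjects who received at least one IP administration, with AEs summarized by the product received and no condition on later assessments. In section 17.8, state that the AE summaries use this set.

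This costs a sentence or two. It needs no new data and leaves the PK analysis unchanged.

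If the sponsor also clarifies efficacy data in the FAS, the clarification should not restrict the FAS to extraction, VAS and pulse. That would exclude a subject who has plasma data, the basis of the primary endpoint, but none of those three.
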